9.6.2.1.2 Day 22 Geometric Mean Titer Analysis

In addition, Day 22 GMTs will be compared between PXVX0317 and placebo treatment groups and will be analyzed via a linear model based on an alpha=0.05. The primary model is an ANOVA, with logarithmically transformed anti-CHIKV SNA titers (\log_{10}) as the dependent variable and treatment group and study site as the fixed effects in the model. The adjusted least square means and their 95% CIs calculated based on the ANOVA will be back transformed and reported as the group GMT values. All tests will be carried out at a two-sided significance level of 0.05 and no adjustment for multiplicity will be applied.

The primary comparison will be in the IEP across both age groups combined. Tests will be repeated in the mITT population as a measure of robustness, along with tests for each population in the separate age strata. No multiplicity adjustment will be made for the analysis of the separate age strata as the primary population will be the combined age groups.

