### **3 STUDY ENDPOINTS**

#### **3.1 Immunogenicity Endpoints**

##### **3.1.1 Coprimary Immunogenicity Endpoints**

- Difference in anti-CHIKV SNA seroresponse rate (PXVX0317 minus placebo) and associated 95% confidence interval (CI) at Day 22.

**Note:** Seroresponse rate (considered the presumptive seroprotection rate) is defined as the percentage of participants who achieve an anti-CHIK SNA titer █.

- Anti-CHIKV SNA GMT and associated 95% CIs at Day 22 for PXVX0317 and placebo.

Each endpoint is summarized for both age strata pooled and for individual age strata, as well as by sex and by race group (white and non-white) and ethnicity group (Hispanic or Latino and Not Hispanic or Latino).

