## 4 POWER AND SAMPLE SIZE CONSIDERATIONS

### 4.1 Sample Size and Power for Immunogenicity

Based on the data from the Phase 2 study (protocol PXVX-CV-317-001), the seroresponse rate for PXVX0317 vaccine is expected to be approximately █ versus <5% for the placebo participants. With an assumed 10% rate of non-evaluable participants, the power to show superiority over placebo with 180 PXVX0317 vaccine and 180 placebo evaluable participants is >99.9% for the combined age groups.

The difference in seroresponse rate between PXVX0317 and placebo groups that is considered clinically relevant is █. With 180 baseline seronegative PXVX0317-treated participants and a target seroresponse rate of █ vs. a rate of 5% for placebo, the width of a two-sided 95% CI would be  $\pm 5.4\%$ . If the target PXVX0317 seroresponse is █, the width would be  $\pm 6.9\%$ . Therefore, the difference in seroresponse rates must be above █ for the lower bound of the 95% CI for the difference to be █.

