## 5.3 Analysis Populations

Analyses are based on the following study populations:

**Randomized Population:** All screened participants who provide informed consent and provide demographic and other screening measurements and are randomized (i.e., have a randomization number assigned within the EDC system). Most baseline summaries and the IP administration summary use the randomized population.

**Exposed Population:** All participants in the randomized population who receive IP.

**Safety Population:** All participants in the exposed population who provide safety assessment data. This generally includes any participant who was not lost to follow-up at Day 1 (baseline), as they are at risk for reporting an SAE. Participants are analyzed as treated (i.e., according to the treatment a participant received, rather than the treatment to which the participant was randomized). All safety analyses use the safety population.

**Modified Intent-to-Treat (mITT) Population:** All randomized participants who are vaccinated and have at least one post-injection anti-CHIKV human SNA assay result. Participants are counted in the group to which they were randomized. Primary and secondary immunogenicity analyses are repeated for the mITT population as a measure of robustness of the results.

**Immunogenicity Evaluable Population (IEP):** The IEP includes all participants in the mITT population who:

- Provide evaluable serum sample results for the relevant post-vaccination time points, and within the required time frames:
  - Day 22: Day 19 through Day 27, inclusive.
- Have no measurable ( $\geq$ LLOQ) anti-CHIKV human SNA assay titer at Day 1 (baseline), i.e., seronegative at baseline. Note that participants with missing Day 1 (baseline) are excluded from IEP.
- Have no important protocol deviation deemed exclusionary or other reason to be excluded as defined prior to unblinding.

The IEP is the primary population for all immunogenicity analyses.

**CHIKV Genotype Subset:** The CHIKV genotype subset includes those IEP participants who received PXVX0317 and are selected for genotype analysis. See Section 8.4.3 for details.

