### 6.1.2 Geometric Mean Titers and Geometric Mean Fold Increase

The superiority of PXVX0317 vaccine immunogenicity over that of placebo is explored further by comparing Day 22 GMTs derived from a linear model with a one-sided alpha=0.025. The primary model is an analysis of variance (ANOVA), with  $\log_{10}$ -transformed anti-CHIKV SNA titers ( $\log_{10}$ ) as the dependent variable and treatment group and study site as the fixed effects in the model. No interaction term is used. The adjusted least square means and their 95% CIs calculated based on the ANOVA are back transformed and reported as the group GMT values. No adjustment for multiplicity is applied. See Section 6.4 for statistical hypothesis, Section 6.9 for multiplicity considerations, and Section 8.4.1.2 for analysis outputs. Identical methods are used for treatment group comparison of GMTs at Days 15 and 183.

Geometric mean fold increase (GMFI) from baseline (Day 1) to Days 15, 22 and 183 is calculated using the difference from Day 1 in  $\log_{10}$ -transformed titers as the dependent variable in the ANOVA model. The adjusted least square means and their 95% CIs calculated based on the ANOVA are back transformed and reported as the group GMFI values. The median, minimum and maximum titers and fold-increases are based on the non-transformed scale.

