**Baseline seropositive rate** is defined as the percentage of participants with anti-CHIKV human SNA assay titer  $\geq$ LLOQ prior to IP administration.

**Body mass index** at screening visit is automatically calculated by EDC as a participant's weight in kg divided by height in  $\text{m}^2$ .

**Anti-chikungunya virus (anti-CHIKV) human SNA assay NT80 (80% neutralizing titer)** is defined as the dilution factor that corresponds to an 80% reduction of luciferase activity compared to virus-only control. Anti-CHIKV SNA titer values below LLOQ are replaced by LLOQ/2 in the immunogenicity analyses including GMT and GMFI. For the 4-fold rise over Day 1 (baseline), values below the LLOQ are replaced with the LLOQ.

**Completion of study** for an individual participant is defined as completion of the Day 183 EOS and any required safety follow-up (i.e., a disposition status of completed).

**Early discontinuation** for an individual participant is defined as completion of the Early Discontinuation/ Withdrawal Visit (i.e., a disposition status other than completed).

**Enrolled/randomized** is defined as receipt of a randomization number assignment within the EDC system.

**Medical history** items entered on the medical history eCRF are considered to predate the study regardless of onset date.

**Medication, concomitant**, is defined as one taken after start of IP administration on Day 1 (baseline) through the end of study. For analysis purposes, any medication which is ongoing or with a stop date that is on or after the start date of IP administration is categorized as a concomitant medication. Partial or missing concomitant medication start and/or end date are imputed according to Section [6.5.2](#).

**Medication, prior**, is defined as one with a stop date within 30 days prior to the screening visit (90 days for blood products) through the start of IP administration on Day 1 (baseline).

**Protocol deviations** are defined by inclusion in the EDC protocol deviation module (participant-level only, not site-level), including monitor-identified deviations as well as Sponsor- and EDC system-identified programmatic deviations. Protocol deviations are classified by category and type (important/not important).

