## 6.4 Statistical Hypotheses

### 6.4.1 Coprimary Immunogenicity Endpoints

The study is a multicenter, randomized, two-arm, active-controlled study to evaluate PXVX0317 vaccine vs. placebo. A successful trial means success on each of the coprimary endpoints: seroresponse ( $H_{A1}$ ) and GMT ( $H_{A2}$ ), both at Day 22 using the IEP. Statistical hypotheses for each of these endpoints are discussed in turn in this section. The familywise error rate is fixed at a two-sided alpha of 0.05 by the requirement that both coprimary endpoints must be met for a successful outcome.

In standard statistical notation, the null and alternative hypotheses are:

$H_0$ :  $H_{A1}$  not met or  $H_{A2}$  not met

$H_A$ :  $H_{A1}$  met and  $H_{A2}$  met

where  $H_{A1}$  and  $H_{A2}$  are the alternative hypotheses for each of the coprimary endpoints as defined below in this section.

The first coprimary endpoint is the treatment group-specific estimates and difference between treatment groups in anti-CHIKV SNA seroresponse rates using a titer of █ at Day 22 in the IEP for both age strata pooled and is tested in two ways. First, the lower bound of the Newcombe hybrid score method two-sided 95% CI on the difference in seroresponse rates between PXVX0317 and placebo must be █. Secondly, the null hypothesis of no difference between seroresponse rate percentages is tested using a two-sided chi-square test with alpha=0.05. In standard statistical notation, the null and alternative hypotheses for the first coprimary endpoint are as follows:

$H_01: (P_{PXVX0317} - P_{placebo}) \leq 0$  using a two-sided chi-square test  
 $H_{A1}: (P_{PXVX0317} - P_{placebo}) > 0$  using a two-sided chi-square test  
where  $P_{PXVX0317}$  is the percentage of PXVX0317 participants and  $P_{placebo}$  is the percentage of placebo participants with seroresponse at a titer of █ at 21 days after vaccination in the IEP for both age strata pooled.

The second coprimary endpoint tests for a significant difference in treatment group-specific Day 22 GMTs in the IEP for both age strata pooled, as derived from a one-sided alpha=0.025 ANOVA with  $\log_{10}$ -transformed anti-CHIKV SNA titers ( $\log_{10}$ ) as the dependent variable and treatment group and study site as the fixed effects. The adjusted least square means and their 95% CIs calculated based on the ANOVA are back transformed and reported as the group GMT values. In standard statistical notation, the null and alternative hypotheses are:

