## **8.4 Immunogenicity Analysis**

Summary statistics for immunogenicity results by scheduled visit for each treatment group are provided for the IEP and mITT populations, unless otherwise specified. Anti-CHIKV SNA seroresponse rates and GMTs are tabulated by visit for each treatment group. Geometric mean fold increase as well as number and percentage of participants meeting anti-CHIKV SNA titers of  $\geq 15$  and 4-fold rise from baseline are also displayed by post-vaccination scheduled visit for each treatment group. Reverse cumulative distribution plots of anti-CHIKV SNA titer versus percentage of participants in each treatment group are generated by scheduled visit for the IEP. Anti-CHIKV SNA GMT are also plotted over time for each treatment group for the IEP.

The primary analysis of all immunogenicity endpoints utilizes the IEP across both age groups combined. As specified for individual endpoints below, primary and secondary immunogenicity analyses of anti-CHIKV SNA seroresponse rates and GMTs are repeated using the mITT population as a measure of robustness of results. All immunogenicity analyses are repeated in the separate age strata for the IEP, and primary and secondary immunogenicity analyses of anti-CHIKV SNA seroresponse rates and GMTs are repeated in the separate age strata for the mITT population as well. No multiplicity adjustment is made for the analysis of the mITT population or of the separate age strata as the primary population is the combined age groups in the IEP.

In addition, the primary immunogenicity endpoints using the IEP across both age groups combined are repeated by sex, by race group (white and non-white), and by ethnicity group (Hispanic or Latino and Not Hispanic or Latino). If the baseline (Day 1) seropositive rate is  $\geq 10\%$ , then subgroup analyses will be performed by baseline serostatus (positive or negative) for coprimary immunogenicity endpoints as well as key secondary seroresponse rate endpoints.

Finally, two types of sensitivity analysis for the coprimary endpoints (difference in anti-CHIKV SNA seroresponse rate between PXVX0317 and placebo at Day 22 and GMTs at Day 22) are performed as described in Section 6.5.3. These endpoints are recalculated using the conservative imputation methods for missing immunogenicity outcome data at Day 22 (i.e., nonresponder analysis and LOCF analysis) and reported for the mITT population to assess the robustness of primary endpoint results to informative missingness.

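### The vaccine arm's GMT and GMFI confidence intervals use a variance pooled with a near-constant placebo arm, so they are too narrow (about 83% coverage in the limit of a constant placebo)

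*SAP*

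**What the plan says.** SAP 3.1.1 defines the second coprimary endpoint as "Anti-CHIKV SNA GMT and associated 95% CIs at Day 22 for PXVX0317 and placebo", so the intervals are part of the endpoint.

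The model is an ANOVA on log10 titre with treatment and site as fixed effects and no interaction. SAP 6.1.2 states that the "adjusted least square means and their 95% CIs calculated based on the ANOVA are back transformed and reported as the group GMT values", and builds the GMFI and its interval the same way from the log10 change since Day 1. SAP 6.4.1 repeats the rule ("The adjusted least square means and their 95% CIs calculated based on the ANOVA are back transformed"), and Protocol 9.6.2.1.2 matches it: "adjusted least square means and their 95% CIs calculated based on the ANOVA will be back transformed and reported as the group GMT values". Neither document mentions a variance per arm, a Welch or Satterthwaite correction, or robust standard errors.

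Three other rules fix how the placebo data will look:
- SAP 5.3 restricts the immunogenicity evaluable population (IEP) to participants without a measurable "anti-CHIKV human SNA assay titer at Day 1 (baseline), i.e., seronegative at baseline".
- Under SAP 6.3, titre "values below LLOQ are replaced by LLOQ/2 in the immunogenicity analyses including GMT and GMFI".
- SAP 4.1 sets the expected vaccine seroresponse rate (redacted) "versus <5% for the placebo participants".

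The method also reaches the age strata, because SAP 8.4 says: "All immunogenicity analyses are repeated in the separate age strata for the IEP".

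**The concern.** An ordinary ANOVA assumes that the residual variance is the same in both arms. Here the design works against that. Placebo recipients start below LLOQ, nearly all should stay there, and each such value is recorded as the same number. Vaccine recipients respond to differing degrees.

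Averaging a near-zero variance with a real one understates the vaccine arm's uncertainty and gives placebo a spread that it does not have. The vaccine GMT with its 95% CI would then be published with less than the stated confidence. The same holds for Days 15 and 183, for every GMFI, and for the age strata. Protocol 1.8.6 expects these data to inform later field studies and raises the possibility of weaker responses in the elderly, so precision in the vaccine arm matters.

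**Working it through.** **The plan's own figure.** The documents give no SD, power or coverage for the GMT analysis. The nearest figure is the seroresponse power of more than 99.9% with 180 evaluable per arm and 5% on placebo. It reproduces for any vaccine rate of about 23.1% or more, and it does not bear on the interval.

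**Inputs from the documents.** Allocation is 1:1, with 180 evaluable per arm and up to 10 sites. The stratum aged 75 or over has about 200 × 0.25 × 0.90 = 45 evaluable per arm.

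**Inputs assumed, because the documents give none.** LLOQ 15 (so LLOQ/2 = 7.5), vaccine log10 SD 0.4–0.6, placebo responder titres, and site sizes. The rate below 5% refers to a redacted seroresponse cut-off, not to the share of placebo at or above LLOQ.

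**Closed form.** Let s_v² be the vaccine variance of log10 titre and r the placebo/vaccine variance ratio. With equal arms:
- pooled variance = s_v²(1 + r)/2
- vaccine CI width relative to the correct width = √((1 + r)/2)
- vaccine CI coverage = 2Φ(1.96·√((1 + r)/2)) − 1

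| r | Relative width | Coverage |
|---|---|---|
| 0 | 0.71 | 83.4% |
| 0.10 | 0.74 | 85.4% |
| 0.25 | 0.79 | 87.9% |
| 0.50 | 0.87 | 91.0% |
| 0.75 | 0.94 | 93.3% |
| 1 | 1.00 | 95.0% |

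**Plausible r.** If a share p of placebo sits at titre T and the rest at 7.5, the placebo variance is p(1 − p)·[log10(T/7.5)]². With vaccine SD 0.5 (variance 0.25):
- p = 2%, T = 100: 0.0196 × 1.125² = 0.0248; r = 0.10; coverage 85.4%
- p = 5%, T = 100: 0.0475 × 1.125² = 0.0601; r = 0.24; 87.7%
- p = 5%, T = 300: 0.0475 × 1.602² = 0.122; r = 0.49; 90.9%
- p = 5%, T = 1000: 0.0475 × 2.125² = 0.214; r = 0.86; 94.1%

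**Simulation of the planned model** (treatment plus 10 sites, equal site weights, vaccine SD 0.4–0.6, 2,000 trials per setting; Monte Carlo standard error about √(0.85 × 0.15/2000) = 0.8 points). Vaccine CI coverage, with 180 per arm and equal sites unless stated:

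| Setting | Coverage |
|---|---|
| No placebo responders | 82–85% |
| 2% at titre 100 | 85–87% |
| 5% at titre 100 | 86–90% |
| 5% at titre 300 | 89–94% |
| 5% at titre 1000 | 91–96% |
| 2% at titre 100 plus 5–20% at titre 30 | 86–90% |
| Unequal sites (4–45 per arm), 0–5% at titre 100 | 86–91% |
| Aged 75 or over (45 per arm), 0–5% at titre 100 | 82–90% |

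A separate simulation with 8,000 trials per setting gave 82.9–83.8% for constant placebo and equal sites.

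**Size on the titre scale** (SD 0.5, constant placebo). For pooled ages the correct half-width is 1.96 × 0.5/√180 = 0.073 log10, a factor of 1.18; the plan gives 0.073 × 0.71 = 0.052, a factor of 1.13. For ages 75 or over the factors are 1.41 (correct) and 1.27 (plan). The plan would also print a placebo interval of ×/÷ 1.10–1.15 (SD 0.4–0.6) around a constant.

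**GMFI.** Every IEP baseline is LLOQ/2, so log10 GMFI is log10 GMT minus a constant, and its interval has the same error.

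**Between-arm test.** With n per arm, the pooled standard error of the difference is √(2 × [(s_v² + s_p²)/2]/n) = √((s_v² + s_p²)/n), which is the unequal-variance value. Simulated coverage for the difference was 93.8–96.2%.

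**Remedies, all settings.** HC3 intervals covered 94.4–97.0%, and arm-specific intervals 94.2–96.2%.

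**The case against.** The strongest objection is that no decision changes. GMT success rests on the between-arm test, and the clinical-relevance criterion uses Newcombe intervals that this does not touch. That stands, and it limits the point to reporting.

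The absolute error for pooled ages is also modest. Around an illustrative GMT of 1000, even constant placebo gives about 885–1130 instead of 847–1180. That stands too; the error is larger in the stratum aged 75 or over, which is not the primary analysis.

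Next, 83% is a limit, and the size depends on quantities that the documents do not give. This is correct. With vaccine SD 0.3 and 5% of placebo at titre 100, for example, r = 0.0601/0.09 = 0.67 and coverage is about 92.7%. The direction of the error is secure as long as placebo varies less than vaccine; its size is not.

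Finally, SAP 6.1 and Protocol 9.3 and 9.6.2 contain general wording about exponentiating each group's log-scale mean and interval, which could mean arm-specific intervals. The planned descriptive statistics and reverse cumulative plots would also make unequal spread visible. But the specific text defines the reported values by the ANOVA, and a single residual variance is the ordinary meaning of that model when nothing else is stated. The general wording shows an ambiguity to settle; it does not supply the missing variance rule.

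**Conclusion.** The concern holds. As written, the vaccine arm's GMT and GMFI intervals will fall short of 95% coverage whenever placebo titres vary less than vaccine titres, and the plan's rules make that likely. Coverage is 83.4% in the constant-placebo limit, about 85–90% with 2–5% of placebo at titre 100, and near nominal only if about 5% of placebo reach titres of several hundred or more. These figures rest on an assumed LLOQ of 15 and a vaccine log10 SD of 0.4–0.6. The placebo interval errs the other way and is too wide. The trial's success criteria are not affected. It should be fixed because the intervals are part of a coprimary endpoint and the repair is cheap.

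**What to change.** In SAP 6.1.2 and 6.4.1 and Protocol 9.6.2.1.2:

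1. Keep the treatment-plus-site ANOVA for the between-arm GMT test.
2. Take the group GMT and GMFI intervals from HC3 standard errors, which preserve the planned least-squares means. The alternative is each arm's own variance, which replaces the site-adjusted mean with the arm's plain geometric mean. Name one method in advance.
3. Prespecify that if every placebo value at a visit is LLOQ/2, placebo is reported as below LLOQ without an interval. This is an exception to the endpoint as defined in SAP 3.1.1, so it needs to be written down.
4. State in SAP 6.1 that the interval in 6.1.2 is the one reported.

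Adding age stratum to the pooled-age model is a separate option. It would change SAP 6.6 and is not needed here; if adopted, it should use the corrected stratum, as SAP 6.3 requires.

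The cost is SAP wording and a few lines of code, with no change to data collection or to any success criterion. The protocol edit goes through the amendment process in Protocol 13.2. The reported vaccine interval becomes wider by up to 1/0.71 = 1.41, about 40% on the log scale.

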## 6 STATISTICAL CONSIDERATIONS

### 6.1 Statistical Considerations

Data summaries are tabulated by appropriate grouping for each analysis population as specified in Section 5.4.

Continuous endpoints are summarized by descriptive statistics including number of non-missing observations (n), mean, SD, median, minimum, and maximum. In the analysis of the anti-CHIKV SNA data as a continuous variable, anti-CHIKV SNA values are logarithmically transformed (base10), and the GMTs and associated 95% CI for each treatment group are computed by exponentiating the corresponding log-transformed means and two-sided 95% CIs. Categorical variables are summarized by frequency counts (n) and percentages of participants (%) in each category, including missing or unknown when appropriate.

Unless otherwise specified, CIs and hypothesis tests are two-sided with 95% confidence (or one-sided with 97.5% confidence).

The reporting conventions to be applied to all tables, listings and figures are included in a living document that accompanies the table and listing shells. All derivations, statistical analyses, summaries, and listings are generated using SAS Version 9.4 or higher (SAS Institute, Inc., Cary, North Carolina, United States).

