## 6.7 Multicenter Study

This study is expected to enroll 400 participants at up to 10 sites in US. Data from all sites will be pooled, but site will be a covariate in the immunogenicity ANOVA models described in Section 6.1.

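### Arm GMTs reported as treatment + site least-square means can differ from the participants' own GMTs, with too narrow a vaccine interval; report them from each arm's own titers

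*SAP*

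**What the plan says.** The Day 22 GMT by arm with its 95% CI is a coprimary endpoint (Protocol 3.3.1, SAP 3.1.1). The estimator is named in the Protocol synopsis (Statistical Methods), Protocol 9.6.2.1.2, and SAP 6.1.2 and 6.4.1. The model has "treatment group and study site as the fixed effects in the model", and SAP 6.1.2 adds "No interaction term is used". On the estimate itself, SAP 6.1.2 says that the model-adjusted means, with their intervals, "are back transformed and reported as the group GMT values". GMFI is built the same way.

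General paragraphs describe the calculation more simply. In SAP 6.1, and likewise in Protocol 9.3 and 9.6.2, GMTs by treatment group are "computed by exponentiating the corresponding log-transformed means and two-sided 95% CIs".

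On sites, SAP 6.7 says: "Data from all sites will be pooled, but site will be a covariate in the immunogenicity ANOVA models". Up to 10 sites are planned, with no minimum size and no rule for pooling small sites. Randomization is stratified by age; site is not named as a stratum (Protocol 3.4.2). No weighting of sites in the least-square means is stated.

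Three further statements matter. The IEP is seronegative at baseline (SAP 5.3). Titers below LLOQ become LLOQ/2 for GMT and GMFI (SAP 6.3). Placebo seroresponse is expected below 5% (SAP 4.1).

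**The concern.** Almost every placebo participant in the IEP should have the same Day 22 value, LLOQ/2. Differences between sites can therefore appear only in the vaccine arm. A model without interaction splits those differences between the arms, so the placebo least-square mean moves with vaccine titers. When sites are uneven and weighted equally, both arm means shift away from the participants' own geometric means. The placebo value can then drop below the lowest titer any participant can have.

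The model also uses one residual variance for two arms with very different spread, which affects the arm intervals.

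What is at stake is the accuracy of the reported coprimary GMTs and intervals. GMFI inherits the same shift, because every IEP baseline is LLOQ/2; a placebo GMFI below 1 could be reported although no titer fell. The age-stratum and other subgroup tables use the same estimator with fewer participants per site.

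**Working it through.** **1. The plan's own figure.** The only power statement concerns seroresponse: above 99.9% with 180 per arm. The vaccine rate is redacted. At an assumed 30% against 5%, two-sided 0.05, power is 99.9997%, so the statement reproduces, and 180/0.9 = 200 per arm. No SD, precision or power is given for GMT.

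**2. Inputs.** From the documents: additive treatment + site model, 1:1 allocation, up to 10 sites, 180 + 180 evaluable, LLOQ/2 substitution, placebo response below 5%. Assumed: site sizes, vaccine SD 0.5 log10, between-site SD 0 or 0.15 log10, and placebo responders at 10 times LLOQ/2. Equal site weights are the SAS default.

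**3. Algebra.** Let placebo be constant at c = log10(LLOQ/2), let v_k be the vaccine mean log10 titer at site k, and let allocation be 1:1 within site. Let V_w be the size-weighted and V_u the unweighted mean of the v_k.
- Estimated treatment difference: V_w - c.
- Fitted placebo mean at site k: (v_k + c)/2 - (V_w - c)/2 = c + (v_k - V_w)/2.
- Placebo least-square mean with equal weights: c + (V_u - V_w)/2.
- The vaccine least-square mean shifts by the same amount, so the difference between arms is unchanged.

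The placebo value is below c whenever smaller sites have lower vaccine titers. The shift is zero when sites are equal.

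**4. Worked example.** Take per-arm site sizes of 40, 40, 30, 30, 10, 10, 6, 6, 4, 4 (total 180) and site deviations from +0.10 to -0.20 log10. The shift is -0.049 log10. The placebo GMT becomes 0.894 × LLOQ/2. The vaccine GMT, in units of LLOQ/2, is reported as 190 against the participants' own 213 (213 × 0.894 = 190).

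**5. Simulation,** 360 evaluable in 10 sites, treatment not balanced within site:

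| Site sizes | Placebo responders | Site SD | Placebo GMT below LLOQ/2 |
|---|---|---|---|
| 5 to 81 | 2% | 0 to 0.15 | about 20-25% of trials |
| 5 to 81 | 4.5% | 0 | about 5% |
| 18 to 54 | 2% | 0 | 5% |
| equal | 2% | 0 | 2% |

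- With sites of 5 to 81, 2% responders and site SD 0, the median value among trials below LLOQ/2 is 7.34 against an assumed 7.5. About 4% of all trials fall more than 5% below.
- The vaccine GMT differs from the participants' own by about -9% to +10% with site SD 0, and by -11% to +13% with site SD 0.15.
- The raw arm GMT is never below LLOQ/2.
- A wider sweep (within-site SD 0.4-0.6, between-site SD 0-0.2, other site patterns, 2% responders) gives 20-34% for strongly uneven, 7-20% for moderately uneven and 2-4% for equal sites. With no placebo responders the share is about half in every pattern, although the shift stays under 3% when sites are equal.

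**6. Interval.** At 2% responders one log10 above the floor, placebo variance is 0.02 × 0.98 = 0.0196.
- Pooled variance: (0.25 + 0.0196)/2 = 0.1348, SD 0.367.
- Model SE with equal sites: 0.367/√180 = 0.0274. Own-arm SE: 0.5/√180 = 0.0373.
- Implied coverage of the vaccine 95% CI: 2Φ(1.96 × 0.0274/0.0373) - 1 = 85%.

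With sites of 5 to 81 the model SE is 0.035, but the equal-weight estimate is itself more variable than the arm mean. Simulated coverage, for the mean at the participating sites, is about 85-90% across these settings. The arm's own titers give about 95%.

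**7. The test.** Site weights cancel in the difference. With equal arms the pooled variance is harmless there: 0.1348 × 2/180 = (0.25 + 0.0196)/180.

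**The case against.** - **The estimator is prespecified and standard.** Site-adjusted least-square means are common. A reader might infer from the general paragraphs that the plan holds two competing definitions of the coprimary GMT. The documents do not support that reading: those paragraphs are conventions, and every endpoint-specific passage names the least-square mean, which governs.
- **Equal weighting is not plan text.** This stands. It is inferred from the software default, and SAP 1 says further derivation detail sits in programmer's notes not seen here.
- **The size rests on assumptions.** This stands. Nothing in the documents suggests sites as uneven as 5 to 81, and the result is sensitive to the placebo responder rate. The shortfall below LLOQ/2 is usually small, and trivial beside a vaccine GMT assumed about 200-fold higher.
- **No decision changes.** This stands. Success is a significant difference between arms, and neither that test nor the GMT ratio is affected.
- **The intervals are wider than needed, so observed-margin weights suffice.** A reader might infer this, because equal weights inflate the model SE relative to observed margins. It does not hold for the vaccine arm. Pooling already makes that interval too narrow, and observed margins narrow it further (SE 0.028 against a true 0.037). Nor do they reliably remove the impossible placebo value: in one simulation of the ≥75 stratum (92 evaluable, sites of 2 to 22), 25.4% of trials stayed below LLOQ/2, against 39.1% with equal weights.

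**Conclusion.** The concern holds as a reporting problem in a coprimary endpoint. As written, the arm GMTs need not equal the participants' own GMTs, the placebo value can be one that no set of participants could produce, and the vaccine interval under-covers.

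The shift in the GMTs depends on uneven sites and on the default weights. It is around 10% for the vaccine GMT in the most uneven setting and nearly vanishes with equal sites. The under-coverage does not depend on uneven sites; it follows from the common variance and is present with equal sites too. LLOQ, titer SD, site sizes and the vaccine response rate are absent or redacted, so every magnitude here is conditional on the stated assumptions.

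A reader might go further and infer that the coprimary GMT test, its error rate or the trial's power is compromised. The algebra shows otherwise. This is a worthwhile, low-cost correction to the reported estimates and does not threaten the trial's conclusion.

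**What to change.** Report each arm's GMT and GMFI with 95% CI from that arm's own log10 titers, as Protocol 9.3 and 9.6.2 and SAP 6.1 already describe for GMT. Keep the treatment + site ANOVA for the between-arm test and the GMT ratio. Apply the same rule to the age-stratum and other subgroup tables. Do not use observed-margin weights as a substitute.

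Costs:
- The Protocol synopsis, Protocol 9.6.2.1.2 and SAP 6.1.2 and 6.4.1 must be aligned. Because the estimator is in the Protocol, this is more than a one-line SAP change.
- The arm GMTs will not divide exactly to the ANOVA ratio. SAP 6.2 plans to present GMT ratios, so the tables need a footnote.
- If no placebo participant responds, the placebo interval has zero width. That reflects the data but should be explained where it is shown.
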